9.5.5.1 Tuberculosis assessment by IGRA

During conduct of the study, the TB assessment by IGRA (QuantiFERON TB Test is recommended) will be performed at study entry (unless an IGRA negative result is available less than 6 weeks prior to the first dose of open-label bimekizumab) and should be repeated at Week 48, Week 96, Week 144, Week 192, and the SFU Visit for all subjects. The test results will be reported as positive, negative, or indeterminate. UCB also recommends that a TB specialist be consulted where TB (latent or active) is suspected or if there are doubts regarding test results. If latent or active TB is identified, subject must undergo appropriate study-specified withdrawal procedures.

9.5.5.2 Tuberculosis questionnaire

The questionnaire “Evaluation of signs and symptoms of tuberculosis” should be used as a source document. The questionnaire will be completed at AS0009 entry, every 12 weeks throughout the study, at Week 208, and at the SFU Visit. The questionnaire will assist with the identification of subjects who may require therapy for TB. A “Yes” response to any of the questions during the study should trigger further assessments to determine if the subject has either LTB or active TB infection.

Subjects with a confirmed latent TB (where no prophylactic treatment is initiated) or active TB infection must be withdrawn from the study (as further detailed in [Section 9.5.5](#)).

9.5.5.3 Tuberculosis management

LTB infection and active TB identified during study

During the study, subjects who develop evidence of LTB infection or active TB must immediately stop further administration of IMP and will be referred to an appropriate TB specialist (pulmonologist or infectious disease specialist) for further evaluation. Evidence of LTB infection is defined as subject’s IGRA test converts to positive or indeterminate (and confirmed indeterminate on repeat), or the subject’s questionnaire or history and physical indicates that TB infection or exposure may have occurred. Evidence of active TB includes, in addition to the aforementioned tests, signs, and symptoms of organ involvement. In either situation, the subject should be carefully assessed by a TB specialist for active TB. Subjects

diagnosed with active TB or LTB infection should be withdrawn from the study and receive appropriate TB or prophylaxis therapy.

If a TB specialist excludes an active TB infection the subject can proceed with the IMP no earlier than 4 weeks after the start of an appropriate prophylactic therapy.

Any presumptive diagnosis or diagnosis of a TB infection is a reportable event. Confirmed active TB must be reported as an SAE. The Investigator is to complete and submit the TB follow-up form provided.

The subject should be transferred to the care of his/her physician and managed according to the best available standard of care. Subjects identified as having converted to active TB during the study must be withdrawn and scheduled to return for the ET Visit as soon as possible, but no later than the next scheduled study visit and complete all ET Visit assessments.

The subject should be encouraged to complete a SFU Visit (20 weeks after the last dose of IMP).

If infection with NTMB is identified during the study, the same procedure as for active TB acquired during the study must be followed.

9.5.6 Pregnancy testing

A urine pregnancy test will be performed at any scheduled or unscheduled visit if there is suspicion of pregnancy and will be confirmed with a serum pregnancy test if the urine test is positive.

Pregnancy test results must be negative prior to administering IMP.

9.5.7 Assessment of suicidal ideation and behavior

Suicidal ideation and behavior will be assessed by trained study personnel using the eC-SSRS. This scale will be used to assess suicidal ideation and behavior that may occur during the study. The visits at which the eC-SSRS assessments will be performed are specified in the schedule of study assessments ([Section 5.2](#)).

The eC-SSRS is a standardized and validated instrument developed for the assessment of the severity and frequency of suicidal ideation and behavior (Posner et al, 2011; Mundt et al, 2010). Subjects respond to standardized clinical questions that are presented in a uniform fashion. The eC-SSRS defines 5 subtypes of suicidal ideation and behavior in addition to self-injurious behavior with no suicidal intent. The eC-SSRS takes approximately 3 to 10 minutes to complete.

10 ASSESSMENT OF EFFICACY

The timing for all assessments described below is specified in [Table 5–1](#) and [Table 5–2](#).

10.1 ASAS20, ASAS40, ASAS 5/6 response and ASAS partial remission

The ASAS20 is defined as an improvement of at least 20% and absolute improvement of at least 1 unit on a 0 to 10 numeric rating scale (NRS) in at least 3 of the 4 following domains:

- PGADA (see [Section 10.7](#))
- Pain assessment (the total spinal pain NRS score; [Section 10.8](#))
- Function (represented by BASFI, [Section 10.4](#))
- Inflammation (the mean of the BASDAI Questions 5 and 6, concerning [REDACTED]
[REDACTED])
- and absence of deterioration in the potential remaining domain (deterioration is defined as a relative worsening of at least 20% and an absolute worsening of at least 1 unit).

The ASAS criteria for 40% improvement are defined as relative improvements of at least 40%, and absolute improvement of at least 2 units on a 0 to 10 NRS in at least 3 of the 4 domains and no worsening at all in the remaining domain.

The ASAS 5/6 response is defined as at least 20% improvement in 5 of 6 domains, including spinal mobility (lateral spinal flexion) and CRP as more objective measures (Brandt et al, 2004).

The ASAS partial remission response is defined as a score of ≤ 2 units on a 0 to 10 unit scale in all 4 domains listed above for ASAS20.

10.2 ASDAS-CRP

The ASDAS is comprised of a number of assessments which are scored by the subject and Investigator and multiplied by a validated formula (van der Heijde et al, 2009) as listed:

- $0.121 \times$ [REDACTED] (BASDAI Question 2 result, [Section 10.3](#))
- $0.058 \times$ [REDACTED] (BASDAI Question 6 result, [Section 10.3](#))
- $0.110 \times$ PGADA ([Section 10.7](#))
- $0.073 \times$ [REDACTED] (BASDAI Question 3 result, [Section 10.3](#))
- $0.579 \times$ (natural logarithm of the CRP [mg/L] + 1)

[REDACTED], PGADA, [REDACTED] are all assessed on a numerical scale (0 to 10 units) (Lukas et al, 2009). The results of these calculations are summed to calculate the ASDAS.

The following definition applies for ASDAS Disease Activity categories:

- ASDAS-ID: ASDAS <1.3
- ASDAS-Moderate Disease: ASDAS $\geq 1.3, < 2.1$
- ASDAS-High Disease activity: ASDAS $\geq 2.1, \leq 3.5$
- ASDAS-very High Disease activity: ASDAS > 3.5

10.3 BASDAI

The most common instrument used to measure the disease activity of AS from the subject's perspective is the BASDAI (Garrett et al, 1994). The BASDAI is a validated self-reported instrument which consists of six 10-unit horizontal NRSs to measure severity of [REDACTED]

[REDACTED] (both severity and duration, respectively) over the last week (van Tubergen et al, 2015). The final BASDAI score ranges from 0 to 10, with lower scores indicating lower disease activity. Question 2 of the BASDAI asks the subject [REDACTED]

[REDACTED] factor in the calculation of ASDAS-CRP. Question 3 of the BASDI asks the subject to [REDACTED]

[REDACTED] factor in the calculation of ASDAS-CRP. Question 6 of the BASDAI asks the [REDACTED], and the score is used as the [REDACTED] factor in the calculation of ASDAS-CRP.

The BASDAI is calculated as follows:

$$\text{BASDAI} = \frac{Q1 + Q2 + Q3 + Q4 + \left(\frac{Q5 + Q6}{2} \right)}{5}$$

10.3.1 [REDACTED] item of the BASDAI

[REDACTED] as a major symptom of AS can effectively be measured with single-item questions such as the BASDAI item (van Tubergen et al, 2002b). This item has shown moderate to good reliability and responsiveness (van Tubergen et al, 2002b). The same minimal clinically important difference (MCID) will be used for the [REDACTED] item of the BASDAI as for the total BASDAI score, ie, a change of 1 unit on the NRS.

10.4 Function – BASFI

The BASFI is a validated disease-specific instrument for assessing physical function (van der Heijde et al, 2005; Calin et al, 1994). The BASFI comprises 10 items relating to the past week. The NRS version will be used for the answering options of each item on a scale of 0 ("Easy") to 10 ("Impossible") (van Tubergen et al, 2015 and van Tubergen et al, 2002a). The BASFI is the mean of the 10 scores such that the total score ranges from 0 to 10, with lower scores indicating better physical function. The MCID used to interpret scores is 7mm on a 0 to 100mm VAS or 17.5% of the Baseline score (Pavy et al, 2005); an MCID of 1 unit will be used for the NRS version.

10.5 BASMI

The BASMI characterizes the spinal mobility of subjects with AS. The BASMI is a disease-specific measure consisting of 5 clinical measures to reflect subject axial status: cervical rotation; tragus to wall distance; lateral spinal flexion; modified Schober test; intermalleolar distance. Each of the 5 movements is scored according to the linear BASMI definition. The mean of the 5 scores provides the BASMI score. The higher the BASMI score the more severe the subject's limitation of movement due to their AS.

10.6 MASES

Enthesitis is assessed via MASES. The MASES is an index that measures the severity (ie, intensity and extent) of enthesitis through the assessment of 13 entheses (bilateral costochondral 1, costochondral 7, anterior superior iliac spine, posterior iliac spine, iliac crest and proximal insertion of the Achilles tendon sites, and the fifth lumbar vertebral body spinous process) (Heuft-Dorenbosch et al, 2003) each scored as 0 or 1 and then summed for a possible score of 0 to 13.

10.7 PGADA

Subjects will score their global assessment of their disease activity in response to the question "How active was your spondylitis on average during the last week?" using a NRS where 0 is "not active" and 10 is "very active" (van Tubergen et al, 2015).

10.8 Total and nocturnal spinal pain

The pain experienced by AS subjects is adequately measured by 2 separate questions: (1) total pain in the spine due to AS (ie, "How much pain of your spine due to spondylitis do you have?"); and (2) pain in the spine at night due to AS (ie, "How much pain of your spine due to spondylitis do you have at night?") (Sieper et al, 2009; van der Heijde et al, 2005; Committee for Proprietary Medicinal Product [CPMP]/EWP/556/95). When responding to each question, the subject is to consider the average amount of pain in the preceding week.

10.9 Short-Form 36-item Health Survey

The SF-36 (Version 2, standard recall) is a 36-item generic health-related quality of life (HRQoL) instrument that uses a recall period of 4 weeks. Items are grouped into 8 domains as follows: Physical Functioning (10 items), Role Physical (4 items), Bodily Pain (2 items), General Health (5 items), Vitality (4 items), Social Functioning (2 items), Role Emotional (3 items), Mental Health (5 items), and 1 item for perceived stability or change in health (Health Transition) during the last year. The concepts represented by these domains contribute to physical, mental, and social aspects of HRQoL.

In addition to domain scores, the Physical Component Summary and Mental Component Summary scores are calculated from the 8 domains (excluding the Health Transition item). Component scores appreciate the impact of each domain on physical and mental health status (Maruish, 2011). Each of the 8 domain scores and the component summary scores range from 0 to 100, with a higher score indicating a better health status. The 2 component summary scores are standardized with a mean of 50 and a standard deviation (SD) of 10 in the general US population.

10.10 ASQoL

The ASQoL, a validated disease-specific 18-item questionnaire, has been developed specifically for measuring HRQoL in subjects with AS (Doward et al, 2003). The ASQoL has been used and has shown to be responsive in axSpA (Barkham et al, 2009; Haibel et al, 2008). The ASQoL score ranges from 0 to 18 with higher score indicating worse HRQoL.

10.11 HADS

The HADS was chosen for its well-established psychometric properties and its use in clinical research on biological therapy in subjects with chronic plaque PSO (Langley et al, 2010; Dauden et al, 2009). The HADS scores for anxiety and for depression range from 0 to 21 with higher scores indicating worse state. A score below 8 is considered to be normal whereas a score of 15 and above is considered severe (Snaith and Zigmond, 1994).

11 ASSESSMENT OF IMMUNOGENICITY

The Investigator or designee will obtain blood samples for measurement of bimekizumab plasma concentrations and antibodies to bimekizumab at the time points specified in [Table 5–1](#) and [Table 5–2](#). When these samples are required at a visit during which the subject is dosed with IMP, the blood samples will be drawn prior to dosing. Samples should be drawn at the same time of the sampling for clinical laboratory tests. The time and date of collection will be recorded in the eCRF. Instructions pertaining to sample collection, processing, storage, labeling, and shipping are provided in the laboratory manual for this study. The presence of antibodies to bimekizumab will be determined using a validated bioanalytical method. Detailed information on sample analysis will be provided in a bioanalytical report.

12 STUDY MANAGEMENT AND ADMINISTRATION

12.1 Adherence to protocol

The investigator should not deviate from the protocol. However, the investigator should take any measure necessary in deviation from or not defined by the protocol in order to protect clinical study subjects from any immediate hazard to their health and safety. In this case, this action should be taken immediately, without prior notification of the regulatory authority, IRB/IEC, or sponsor.

After implementation of such measure, the investigator must notify the CPM of the sponsor within 24 hours and follow any local regulatory requirements.

12.2 Monitoring

UCB (or designee) will monitor the study to meet the sponsor's monitoring SOPs, ICH-GCP guideline, and applicable regulatory requirements, and to ensure that study initiation, conduct, and closure are adequate. Monitoring of the study may be delegated by UCB to a CRO or a contract monitor.

The Investigator and his/her staff are expected to cooperate with UCB (or designee) and to be available during the monitoring visits to answer questions sufficiently and to provide any missing information. The Investigator(s)/institution(s) will permit direct access to source data/documents for study-related monitoring, audits, IRB/IEC review, and regulatory inspection(s).

The Investigator will allow UCB (or designee) to periodically review all eCRFs and corresponding source documents (eg, hospital and laboratory records for each study participant). Monitoring visits will provide UCB (or designee) with the opportunity to evaluate the progress of the study, verify the accuracy and completeness of CRFs, ensure that all protocol requirements, applicable authorities' regulations, and Investigator's obligations are being fulfilled, and resolve any inconsistencies in the study records.

12.2.1 Definition of source data

All source documents must be accurate, clear, unambiguous, permanent, and capable of being audited. They should be made using some permanent form of recording (ink, typing, printing, optical disc). They should not be obscured by correction fluid or have temporary attachments (such as removable self-stick notes). Photocopies of CRFs are not considered acceptable source documents.

Source documents are original records in which raw data are first recorded. These may include hospital/clinic/general practitioner records, charts, diaries, x-rays, laboratory results, printouts, pharmacy records, care records, ECG or other printouts, completed scales, or quality of life questionnaires, for example. Source documents should be kept in a secure, limited access area.

Sponsor or designee will review to ensure that computerized source documents produced by the site are compliant with Food and Drug Administration (FDA) Part 11 requirements and document appropriately. Source documents that are computer generated and stored electronically must be printed for review by the monitor (eg, ECG reports). Once printed, these copies should be signed and dated by the Investigator and become a permanent part of the subject's source documents. The Investigator will facilitate the process for enabling the monitor to compare the content of the printout and the data stored in the computer to ensure all data are consistent.

Electronic data records must be saved and stored as instructed by UCB (or designee).

12.2.2 Source data verification

Source data verification ensures accuracy and credibility of the data obtained. During monitoring visits, reported data are reviewed with regard to being accurate, complete, and verifiable from source documents (eg, subject files, recordings from automated instruments, tracings [ECG], x-ray films, laboratory notes). All data reported on the CRF should be supported by source documents, unless otherwise specified in [Section 12.2.1](#).

12.3 Data handling

12.3.1 Case Report form completion

This study will use electronic data capture (EDC); the Investigator is responsible for prompt reporting of accurate, complete, and legible data in the eCRF and in all required reports.

This study will also use an electronic device (Site Tablet) to capture patient reported outcomes.

Serious AE reporting will be done using the SAE Report Form (see [Section 9.1.13](#)) while also entering the event in the appropriate eCRF section. The safety database and the clinical database will be reconciled during the study and discrepancies will be corrected as needed.

The Investigator should maintain a list of personnel authorized to enter data into the eCRF. Access to the EDC will be given after training has been received. A training certificate will be provided and filed.

Detailed instructions on the use of the EDC will be provided in the eCRF Completion Guidelines.

Corrections made after the Investigator's review and approval (by means of a password/electronic signature) will be re-approved by the Investigator. Any change or correction to the eCRF after saving must be accompanied by a reason for the change.

12.3.2 Database entry and reconciliation

Case Report forms/external electronic data will be entered/loaded into a validated electronic database using a clinical data management system (CDMS). Computerized data cleaning checks will be used in addition to manual review to check for discrepancies and to ensure consistency of the data. This study is performed using EDC: the data are entered into the electronic CRFs once and are subsequently verified.

An electronic audit trail system will be maintained within the CDMS to track all data changes in the database once the data have been saved initially into the system or electronically loaded. Regular backups of the electronic data will be performed.

12.3.3 Subject Screening and Enrollment log/Subject Identification Code list

The subject's screening and enrollment will be recorded in the Subject Screening and Enrollment Log.

The Investigator will keep a Subject Identification Code list. This list remains with the Investigator and is used for unambiguous identification of each subject.

The subject's consent and enrollment in the study must be recorded in the subject's medical record. These data should identify the study and document the dates of the subject's participation.

12.4 Termination of the study

UCB reserves the right to temporarily suspend or prematurely discontinue this study either at a single site, multiple sites, or at all sites at any time for reasons including, but not limited to, safety or ethical issues, inaccurate or incomplete data recording, noncompliance, or unsatisfactory enrollment with respect to quality or quantity.

If the study is prematurely terminated or suspended, UCB (or its representative) will inform the Investigators/institutions and the regulatory authority(ies) of the termination or suspension and the reason(s) for the termination or suspension, in accordance with applicable regulatory requirement(s). The IRB/IEC should also be informed and provided with reason(s) for the termination or suspension by the sponsor or by the investigator/institution, as specified by the applicable regulatory requirement(s). In addition, arrangements will be made for the return of all unused IMP and other material in accordance with UCB procedures for the study.

12.5 Archiving and data retention

The Investigator will maintain adequate records for the study, including eCRFs, medical records, laboratory results, Informed Consent documents, drug dispensing and disposition records, safety reports, information regarding participants who discontinued, and other pertinent data.

All essential documents are to be retained by the investigator until at least 2 years after the last approval of a marketing application in an ICH region and until there are no pending or contemplated marketing applications in an ICH region, or at least 2 years have elapsed since the formal discontinuation of clinical development of the IMP. These documents should be retained for a longer period, however, if required by the applicable regulatory requirement(s) or by an agreement with UCB (CPMP/ICH/135/95, 2002 [Section 4.9.5]). The Investigator will contact UCB for authorization prior to the destruction of any study records or in the event of accidental loss or destruction of any study records. The Investigator will also notify UCB should he/she relocate or move the study-related files to a location other than that specified in the sponsor's trial master file.

12.6 Audit and inspection

The Investigator will permit study-related audits mandated by UCB, after reasonable notice, and inspections by domestic or foreign regulatory authorities.

The main purposes of an audit or inspection are to confirm that the rights and well-being of the subjects enrolled have been protected, that enrolled subjects (ie, signing consent and undergoing study procedures) are appropriate for the study, and that all data relevant for the evaluation of the IMP have been processed and reported in compliance with the planned arrangements, the protocol, investigational site, and IRB/IEC SOPs, ICH GCP, and applicable regulatory requirements.

The Investigator will provide direct access to all study documents, source records, and source data. If an inspection by a regulatory authority is announced, the investigator will immediately inform UCB (or designee).

12.7 Good Clinical Practice

Noncompliance with the protocol, ICH-GCP, or local regulatory requirements by the Investigator, institution, institution staff, or designees of the Sponsor will lead to prompt action by UCB to secure compliance. Continued noncompliance may result in the termination of the site's involvement in the study.

13 STATISTICS

A description of statistical methods follows and will be described in more detail in the Statistical Analysis Plan.

13.1 Definition of analysis sets

The Enrolled Set (ES) will consist of all subjects who have given informed consent for AS0009.

The Safety Set (SS) will consist of all subjects who receive at least 1 dose of the IMP in AS0009.

The Full Analysis Set (FAS) will consist of all enrolled subjects who receive at least 1 dose of the IMP and have a valid measurement for at least 1 efficacy variable at AS0009 study entry.

13.2 General statistical considerations

Summary statistics will consist of frequency tables for categorical variables. For continuous variables, summary statistics will consist of number of available observations, arithmetic mean, standard deviation (SD), median, minimum, and maximum unless stated otherwise.

Two subpopulations will be defined for this study. Subpopulation 1 will consist of all subjects who do not receive rescue therapy according to the criteria outlined in [Section 5.1.1](#).

Subpopulation 2 will consist of all subjects who receive rescue therapy according to the criteria outlined in [Section 5.1.1](#). Analyses of the primary and secondary variables will also be done on both subpopulations.

Changes from Baseline will be calculated relative to the Baseline of studies AS0008. Variables measured at the start of AS0009 will be referred to as AS0009 entry values.

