4.2 Secondary variables

4.2.1 Secondary safety variable

The secondary safety variable is the withdrawal due to TEAEs.

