4.2.2 Secondary efficacy variables

The secondary efficacy variables are:

- ASAS40 response at Week 48
- ASAS20 response at Week 48
- Change from Baseline of AS0008 in BASDAI at Week 48

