3.6.2 Safety Set

The Safety Set (SS) will consist of all subjects in the ES who received at least one dose of study medication in AS0009.

All safety variables will be summarized for the SS. Pharmacokinetic and immunological variables will also be summarized on the SS.

Two sub-populations of the SS will be defined for this study: Sub-population 1 will consist of all subjects in the SS who took no concomitant rescue medication in AS0009, and Sub-population 2 will consist of all subjects in the SS who took concomitant rescue medication in AS0009, as outlined in [Section 6.5](#). Rescue medications will be identified in the study database using the flag collected in the electronic case report form (eCRF). Concomitant medications are defined in [Section 6.4](#).

Selected summaries of the primary and secondary safety variables will be repeated for both SS Sub-populations only in the event that the number of subjects receiving rescue medication is $\geq 10\%$ of the total number of subjects in the SS.

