3.10 Changes to protocol-defined analyses

The following changes have been made to the protocol-defined analyses:

- Change from AS0009 EV for safety variables will no longer be presented, since the EV assessment is made after 36 or 48 weeks of bimekizumab treatment and there is unlikely to be any further important change.
- Change from AS0008 Baseline and AS0009 EV for laboratory variables will not be presented, due to a change in laboratory vendor between AS0008 and AS0009. Laboratory Baseline has been defined as the earliest value in AS0009 at or prior to AS0009 Week 12.
- Summaries of ASAS40, ASAS20 and ASAS5/6 response at each post-AS0008 Baseline visit have been added for subjects who were responders at AS0008 Week 12. These summaries include all post-AS0008 Baseline visits through to AS0009 Week 208, for subjects in the FAS for AS0009, and will be used to assess maintenance of response.
- The protocol describes the FAS as consisting of all enrolled subjects who receive at least 1 dose of IMP and have a valid measurement for at least 1 efficacy variable at AS0009 study entry. This has been updated to include all subjects in the ES who received at least one dose of study medication in AS0009 and have a valid measurement for at least one efficacy variable at a scheduled visit (excluding SFU visits) after AS0009 EV. This was updated in order to identify subjects who have had assessments during AS0009 and which contribute to any of the efficacy analyses.
- Summaries by randomized treatment in AS0008 will not be produced, as subjects will have been on a constant dose of bimekizumab 160mg or 320mg for at least 36 weeks prior to AS0009 entry. Maintenance of response displays will be split by treatment sequence across AS0008 and AS0009. Safety displays using AS0008 information will incorporate exposure in AS0008.
- The protocol defines subgroups based on ‘Concomitant non-steroidal anti-inflammatory drug (NSAID) status at AS0009 entry. This has been updated to ‘Concomitant NSAID status at start of AS0008’.
- The protocol stated that all safety analysis would be performed for both Sub-populations; instead only key safety analyses will be repeated by Sub-population as identified in [Section 10](#). These analyses will be performed only in the event that the number of subjects receiving rescue medication is $\geq 10\%$ of the total number of subjects in the SS.

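### The SAP drops the protocol's Week 48 secondary efficacy analyses by rescue status, and SAP 3.10 declares the narrowing for safety only

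*Protocol*

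**What the plan says.** Protocol 13.2 defines two subpopulations, subjects who do not and subjects who do receive rescue therapy under Protocol 5.1.1, and then commits: "Analyses of the primary and secondary variables will also be done on both subpopulations". Protocol 4.2 sets out the secondary variables. On the safety side, "The secondary safety variable is the withdrawal due to TEAEs". On the efficacy side there are three, beginning with "ASAS40 response at Week 48" and followed by ASAS20 response and BASDAI change at the same visit. Protocol 13.3.1 adds a separate commitment that all safety analyses will be run in both subpopulations.

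The SAP handles this in 3.6.2, under the Safety Set: "Two sub-populations of the SS will be defined for this study". Membership depends on whether any concomitant rescue medication was taken in AS0009, with no time limit. The output is restricted: "Selected summaries of the primary and secondary safety variables will be repeated for both SS Sub-populations only in the event" that at least 10% of the Safety Set received rescue. SAP 3.10, which lists departures from the protocol, says: "The protocol stated that all safety analysis would be performed for both Sub-populations; instead only key safety analyses will be repeated by Sub-population".

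**The concern.** The protocol sentence stands under general statistical considerations, so on its face it covers efficacy as well as safety. The SAP keeps a reduced safety part, and the efficacy part disappears without comment.

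This is a single-arm study in which the investigator may add NSAIDs, conventional DMARDs, short steroid courses or joint injections at any time (Protocol 7.8.1). The protocol's introduction describes NSAIDs as often acting quickly on pain and stiffness, and those symptoms feed the ASAS domains and the BASDAI. The rescue split was the only efficacy display in the protocol that addressed added therapy. Without it, a Week 48 responder who had started rescue is counted with all other responders, and no table shows how many there are. A reader who checks SAP 3.10 for departures from the protocol would not learn that a specified efficacy analysis had been removed.

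**Working it through.** There is no sample size, power or test to reproduce, because the study is descriptive. The check is a comparison of texts, followed by a short illustration of scale.

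**Comparison**

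1. *Scope of the commitment.* Protocol 13.2 covers primary and secondary variables. Protocol 4.2.2 makes ASAS40, ASAS20 and BASDAI change at Week 48 secondary. The commitment therefore includes them. Protocol 13.4 places efficacy summaries in the FAS, but 13.2 describes the subpopulation analyses as additional, so the two sections do not conflict.
2. *What the SAP repeats by sub-population.* Exposure (SAP 10.1), and the TEAE overview, all TEAEs and serious TEAEs (SAP 10.2). All are subject to the 10% condition. The overview includes TEAEs leading to discontinuation, so the secondary safety variable is still reported by sub-population when the condition is met.
3. *What the SAP plans for efficacy.* SAP 8.2 summarizes the secondary efficacy variables in the FAS by treatment group at completion of AS0008 and overall. SAP 8.3 has no rescue split. SAP 4.8 and 8.4 use region, past TNF inhibitor exposure and NSAID status at the start of AS0008. SAP 4.6 declares an efficacy subset not applicable. The non-responder rule in SAP 4.2.1 covers missing data and dropout and does not mention rescue.
4. *What is declared.* The sub-population entry in SAP 3.10, and the matching entries in the SAP Amendment 1 log, concern safety variables only. Neither mentions efficacy by rescue status.

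**Trigger and precision**

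- If all 285 subjects are in the Safety Set, the trigger is 0.10 × 285 = 28.5, so 29 subjects.
- 95% half-width for a proportion of 0.5: 1.96 × √(0.25/n). For n = 29 it is 0.182 (18 points). For the other 256 it is 0.061 (6 points).

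**Scale, on assumed values**

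Let pN and pR be the response rates in never-rescued and rescued subjects, and n2 the number rescued out of N. The FAS rate is [(N − n2) × pN + n2 × pR] / N, so

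never-rescued rate − FAS rate = (n2/N) × (pN − pR).

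With N = 285 and pN assumed to be 60%:

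| Rescued | n2 | pR = 60% | pR = 40% | pR = 20% |
|---|---|---|---|---|
| 10% | 29 | 0 | 2.0 points | 4.1 points |
| 20% | 57 | 0 | 4.0 points | 8.0 points |
| 30% | 86 | 0 | 6.0 points | 12.1 points |

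None of the rescue fractions or response rates comes from the documents. The table shows only that the gap depends on both, and that it is zero whenever the two groups respond alike.

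**The case against.** The strongest reply is that little is lost. The primary objective is safety, the study has no formal sample size, and the groups are formed after entry, so an efficacy comparison between them has no causal meaning. The safety reduction is openly declared. Rescue use is summarized by category and listed by subject with start dates (SAP 6.5), and efficacy is listed for the FAS (SAP 8), so the split could be reconstructed. The protocol's own definition has no time limit either: a subject first rescued long after Week 48 would fall in the rescued group although the Week 48 response was free of rescue. Finally, SAP 4.3 schedules an interim analysis with all but the COVID-19 outputs once the last subject reaches Week 108, and SAP Amendment 2 followed review of its results. A Week 48 cut-off chosen now is chosen after the data were seen.

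Most of this stands, and it limits the point. A reader might infer four stronger things that the documents do not support:

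- *That the lost analysis would have shown response on bimekizumab alone.* Protocol 5.1.1 describes rescue as treatment on top of medications already received in AS0008, so never-rescued subjects may still be taking NSAIDs or DMARDs.
- *That the split cannot be seen at all.* What is missing is a planned summary. The listings remain.
- *That the whole reduction is undeclared.* Only the efficacy part is.
- *That response is overstated by some number of points.* If 10% to 30% were rescued and half of them responded, 5 to 15 points of the ASAS40 rate would come from rescued responders (0.10 × 0.5 and 0.30 × 0.5). That is a share of responders under assumed values. It is neither a bias nor the gap that the split would reveal.

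The reply does not explain why an efficacy analysis named in the protocol is absent from the SAP and from the SAP's list of changes. Listings do not replace a specified summary.

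**Conclusion.** The protocol and SAP conflict, and the point holds for efficacy only. Protocol 13.2 commits to the Week 48 secondary efficacy variables in both rescue subpopulations. The SAP contains no such output, and SAP 3.10 does not record its removal. As planned, no summary separates Week 48 response with and without added rescue therapy.

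No effect size can be given, because the documents state neither a rescue rate nor a response rate. The gap may be zero. The conclusion rests on reading the variables in 13.2 as those of Protocol 4.1 and 4.2, which is the natural reading. The matter should be corrected, but it does not touch the primary safety objective.

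**What to change.** Add to SAP 8.2 descriptive summaries of ASAS40, ASAS20 and BASDAI change at Week 48 in the FAS by rescue status, using the imputation already specified in SAP 4.2.1. Classify a subject as rescued if the first rescue start date is on or before the Week 48 visit, because the any-time definition in SAP 3.6.2 would put subjects first rescued after Week 48 in the rescued group. State the 10% trigger on the same basis, that is, rescue up to Week 48 as a share of the FAS. Record in SAP 3.10 that the time limit is a refinement of the protocol definition. If the sponsor prefers not to produce these tables, list and justify the removal in SAP 3.10.

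A further analysis counting rescue as non-response would be optional. Protocol 13.8 does not promise it, and its absence is not a defect.

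The cost is a few tables and one new derivation. The eCRF rescue flag and start dates exist, but the flag alone does not give status at Week 48, and partial start dates must first pass through the rules in SAP 4.2.3. The display is descriptive only, imprecise for a rescued group near the trigger, and should be labelled as added after the interim results were reviewed.
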